1. STUDY OBJECTIVES/HYPOTHESIS

Primary Objective

To evaluate whether established parenteral nutrition associated liver disease (PNALD) can be reversed or its progression halted by using a parenteral fat emulsion prepared from fish oil (omega-3 fatty acid emulsion, Omegaven®) as measured by normalization or decrease of serum levels of hepatic enzymes.

Secondary Objective

To assess the safety profile of the intravenous omega-3 fatty acid emulsion (Omegaven®).

## 2. BACKGROUND

Patients suffering from short bowel syndrome require life-saving parenteral nutrition (PN). One of the major complications of this essential therapy is PNALD, especially in infants and children. This liver injury affects the majority of infants and children on long term PN and may progress to liver failure, liver transplantation or ultimately death. A number of causes of PNALD have been proposed, including the use of intravenous fat emulsions.

PN provides intravenous nutritional supplementation for patients unable to absorb adequate enteral nutrients secondary to insufficient intestinal length or decreased functionality. PN contains the macronutrient building blocks of the human diet in their most elemental forms (amino acids and dextrose) and is commonly administered with a lipid emulsion to avoid essential fatty acid deficiency and to provide a calorically dense source of non-protein calories. In addition, PN contains the essential micronutrients (electrolytes, trace elements, and vitamins) to provide an optimal nutritional regimen. Before the development of PN, patients with insufficient gastrointestinal absorptive function commonly died of starvation and subsequent complications of malnutrition. Today many patients (30,000) patients are permanently dependent on PN for survival. However, PN continues to be associated with hepatic injury that occurs at an unpredictable rate and includes both biochemical (elevated serum aminotransferases and alkaline phosphatase) and histological alterations such as steatosis, steatohepatitis, lipodosis, cholestasis, fibrosis, and cirrhosis.

Parenteral lipid emulsions in the United States are soy-based products which are rich in omega-6 fatty acids. These emulsions have been implicated in predisposing patients to PNALD because of their phytosterol content, which is thought to have a deleterious effect on hepatic biliary secretion and cause accumulation of lipids in the liver. On the other hand, animal studies have shown that intravenous fat emulsions prepared from fish oil, which are high in omega-3 fatty acids, do not impair bile flow and may actually diminish fat accumulation in hepatocytes. Fish oil based emulsions (ie, Omegaven) are available in Europe. Due to regulatory and manufacturing limitations, these products are not available to patients in the US unless their physician petitions the Food and Drug Administration for permission to import them on a compassionate use basis.

Children's Hospital, Boston has published data regarding the use of Omegaven in patients with PNALD.

It has been their experience, that through the use of Omegaven instead of conventional lipid emulsions, that the biochemical tests of liver function improved significantly.

There has been no documented case of heavy metal contamination with the use of Omegaven. There is no discussion in the literature of there being any worry or risk of this happening.

## 3. DESIGN

This is a compassionate use protocol for patients with PNALD who have failed traditional treatment to receive Omegaven through an IND.

### TARGET POPULATION SPECIFICS

We will be enrolling up to 10 patients 0- less than 18 years of age who have Parenteral Nutrition Associated Liver Disease. These patients will have been on traditional TPN for on average 2-4

weeks and will remain on TPN using Omegaven until they no longer need TPN or are sent for short bowel or liver transplant.

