#### Inclusion Criteria

1. The patient will be PN dependent and unable to meet nutritional needs solely by enteral nutrition.
2. Patient will be <18 years of age.
3. Direct bilirubin > 2.0mg/dl
4. The patient must have failed standard therapies to prevent progression his/her liver disease.

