### Institutional Review Board (IRB) Review and Informed Consent

This protocol, and any subsequent modifications, will be reviewed and approved by the Pediatric IRB at The Children's Mercy Hospital & Clinics.

Permission/assent will be obtained after [name] has decided that a patient would benefit from Omegaven therapy and all other standard therapies have been exhausted. Permission/assent will be obtained in person and as the subjects will all be inpatients, will most likely be obtained in the NICU or PICU. Without this treatment, the next step for these patients is short bowel or liver transplant.

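### The entry rules do not ensure the established liver disease named in the objective, so improvement of an unconfirmed or transient elevation can be counted as reversal

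*Protocol*

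**What the plan says.** - **Objective** (Protocol, section 1): "To evaluate whether established parenteral nutrition associated liver disease (PNALD) can be reversed or its progression halted", "as measured by normalization or decrease of serum levels of hepatic enzymes". No size of decrease and no time point are given there.
- **Background** (section 2): "This liver injury affects the majority of infants and children on long term PN". The same section says that the injury appears at a rate that cannot be predicted.
- **Population** (Target Population Specifics): at most 10 patients under 18. "These patients will have been on traditional TPN for on average 2-4" weeks. Treatment runs until TPN can be stopped or the patient goes to transplant.
- **Inclusion Criteria**: besides age, "The patient will be PN dependent and unable to meet nutritional needs solely by enteral nutrition"; "Direct bilirubin > 2.0mg/dl"; and "The patient must have failed standard therapies to prevent progression his/her liver disease".
- **Exclusion Criteria**: the liver-related exclusion names four chronic conditions. Acute or temporary causes of cholestasis are not listed.
- **Consent** (Institutional Review Board (IRB) Review and Informed Consent): permission is sought once the physician judges that the patient would benefit and standard options are used up. It adds: "Without this treatment, the next step for these patients is short bowel or liver transplant".
- **Statistical Considerations**: none are offered, on the ground of compassionate use. No comparison group is described anywhere.

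**The concern.** The objective and the consent section describe advanced disease, with standard options used up and transplant next. The population section describes patients who, on average, have had a few weeks of TPN. What should link the two is a set of entry rules that identifies established disease. The one rule that can be measured is a bilirubin threshold, which a single reading can satisfy.

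The stake is how the results are read. In an uncontrolled series where any fall in enzymes counts, a patient whose laboratory values would have settled anyway looks the same as a patient whose established disease was reversed. The consent section's general statement of prognosis adds to this, because it invites the reader to credit the drug with every transplant avoided.

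**Working it through.** The protocol derives no figure that could be reproduced. It gives no error rate, power or effect size, and 10 is a cap on enrolment. The check is a comparison of sections, followed by one illustration.

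**Step 1. Is the disease state in the objective secured at entry?**

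| Feature implied by the objective or prognosis | Matching entry rule | Measurable? |
|---|---|---|
| Liver disease present | Direct bilirubin above 2.0 mg/dl | Yes |
| Disease established, not temporary | No repeat value, trend or minimum PN exposure | No rule |
| Standard therapies failed | Inclusion criterion 4 | No: neither the therapies nor failure is defined |
| Need for PN | Inclusion criterion 1 | By clinical judgement |
| Other causes absent | Four chronic conditions excluded | Yes, but acute causes are not covered |
| Transplant is the next step | Physician's decision | No stated standard |

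The row that carries the word *established* has no rule behind it.

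**Step 2. Does the failed-therapy criterion fill the gap?** Only in part. It is a real requirement. But with 2-4 weeks of TPN as the average, a typical patient must develop the liver disease, receive standard therapies and fail them within that time. The protocol does not say how failure is recognised over so short a period. The criterion therefore makes the need to reconcile the sections more evident.

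**Step 3. How could improvement arise without a drug effect?**
- A patient selected on a value above a cut-off is, on average, nearer a temporary peak than the patient's own usual level, so later values tend to be lower.
- An elevation that would have resolved does so during treatment.
- Some patients are expected to come off TPN, which the Background associates with the injury.

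**Step 4. What could this do in 10 patients?** The documents give no rate of spontaneous improvement, so the rate p below is an assumption across a wide range. With n = 10 and no drug effect, the expected number of apparent reversals is 10 × p, and

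P(at least 3 of 10) = 1 − Σ (k = 0 to 2) C(10,k) p^k (1 − p)^(10−k).

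| Assumed p | Expected apparent reversals | P(at least 3 of 10) |
|---|---|---|
| 0.1 | 1 | 0.07 |
| 0.2 | 2 | 0.32 |
| 0.3 | 3 | 0.62 |
| 0.5 | 5 | 0.95 |

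For p = 0.2, the sum is 0.107 + 0.268 + 0.302 = 0.678, and 1 − 0.678 = 0.322.

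The last row is not far-fetched under a rule that counts any decrease. If one enzyme only fluctuates at random about a stable level, a later reading is below an earlier one half the time. The table shows how sensitive an uncontrolled series of this size is to p. It does not estimate p for this trial.

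**The case against.** The strongest reply is that the entry rules contain much more than a bilirubin value. PN dependence and failed standard therapies are required. Data Collection Procedures speaks of a patient whose clinical course has moved towards needing the drug, and a physician decides on eligibility. Consent follows only when standard options are used up. This stands. A reader might infer that one laboratory value is enough for entry, and the documents do not support that. What remains is that none of these further conditions is defined in a way that a second reader could apply.

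The 2-4 weeks is a descriptive average and not a criterion, and the protocol nowhere says that disease at that stage is early or transient. This also stands. The documents show a mismatch that they leave unexplained. They do not show that these patients have mild disease.

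Selection is on bilirubin, while the objective is measured on enzymes. This stands in part. Regression to the mean carries over to enzymes only as far as the two move together, and the documents do not say how far that is. Natural resolution does not depend on this link, nor does random fluctuation under a rule that counts any decrease.

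Finally, this is an access protocol with no publication planned. But section 1 states an evaluative objective, and Publication of Research Findings leaves the possibility open, so the interpretation still matters. A statistical analysis plan could set the analysis groups, but the conflict between objective, population and prognosis lies in the protocol itself.

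**Conclusion.** The point holds in a limited form: entry does not ensure the disease state that the objective names. Patients with unconfirmed or temporary elevation *can* be enrolled, and with no comparator and no required size of decrease, their improvement *can* be counted as reversal.

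The size is unknown. A reader might infer that transient cholestasis *is* being enrolled and reported as reversed, or might name the share of the 10 patients affected. The documents support neither, because they give no rate of transient elevation and plan no formal reversal rate. The only firm arithmetic is that each affected patient is 1/10, or 10 percentage points, of a full group of 10, and more if fewer enrol.

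Nor does the protocol say that every patient would otherwise be transplanted in all circumstances, since it also foresees patients leaving TPN. The consent sentence is nevertheless worded for all patients, without that qualification. The conclusion assumes that no fuller definition of established disease or failed therapy exists in material not at hand.

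**What to change.** Neither change alters who may receive the drug.

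1. **Reconcile the text.** Bring section 1, Target Population Specifics, the Inclusion Criteria and the consent section into agreement, stating what *established* and failed standard therapy mean. Alternatively, drop *established* from the objective and limit the transplant prognosis to patients with documented progression.
2. **Report the pre-treatment course.** For each patient, give the duration of PN and all available bilirubin and hepatic-enzyme values before the first dose, taken from the medical record. Base any conclusion about reversal of established disease on patients whose pre-treatment values show persistent elevation on more than one date, at an interval that the sponsor fixes in advance. List the remaining patients separately with their outcomes.

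The cost is protocol wording and retrieval of routine results already on file. The main drawback is that the group supporting the conclusion, at most 10 patients to begin with, may shrink. Confirmation and separate listing reduce the bias from selection at a temporary peak. They do not replace a control group, so improvement among confirmed patients should still be described as observed change.

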## STATISTICAL CONSIDERATIONS

As this is a compassionate use protocol, there are no real statistical considerations. All subjects who could benefit from Omegaven will be included.

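### The primary measure counts only enzyme change, so a patient sent for liver transplant or who dies after an enzyme fall can be scored as PNALD reversed or halted

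*Protocol*

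**What the plan says.** Section 1 of the protocol (Study Objectives/Hypothesis) asks whether established PNALD "can be reversed or its progression halted by using a parenteral fat emulsion prepared from fish oil", and fixes the yardstick in the same sentence: "as measured by normalization or decrease of serum levels of hepatic enzymes". It gives no size of decrease, no time point and no clinical component. The only other objective is safety.

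Target Population Specifics sets how long treatment lasts: patients "will remain on TPN using Omegaven until they no longer need TPN or are sent for short bowel or liver transplant". It does not say how either exit bears on the primary measure, and it does not mention death.

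Two other places say what a bad outcome is. Section 2, Background, says the liver injury "may progress to liver failure, liver transplantation or ultimately death". The section on IRB review and informed consent adds: "Without this treatment, the next step for these patients is short bowel or liver transplant".

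Statistical Considerations supplies no counting rule: "As this is a compassionate use protocol, there are no real statistical considerations".

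**The concern.** The objective is about progression, but the measure cannot register the events that the protocol itself names as progression. Weaning from TPN and referral for liver transplant are opposite results for the liver. Under the stated measure they are told apart only if the enzymes happen to differ. If enzymes fell in both patients, both satisfy the criterion.

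At stake is the meaning of any summary of response. The clearest evidence that the disease was not halted cannot make a patient a failure. If enzymes had fallen first, that patient may be listed as a success.

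**Working it through.** The protocol gives no alpha, power, effect size or derived sample size, so there is no figure to reproduce. The check is mainly a reading of the text.

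**Step 1. Set the statements side by side.**

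| Element | What the protocol fixes | Where |
|---|---|---|
| Aim | PNALD reversed, or progression halted | Section 1, Primary Objective |
| Measure | Hepatic enzymes normalize or decrease | Section 1, Primary Objective |
| What PNALD progresses to | Liver failure, liver transplantation, death | Section 2, Background |
| What follows without treatment | Short bowel or liver transplant | IRB Review and Informed Consent |
| How treatment ends | TPN no longer needed, or sent for short bowel or liver transplant | Target Population Specifics |
| Rule linking exit or death to the measure | None | Statistical Considerations adds none |

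**Step 2. Follow one patient through.** Enzymes fall on Omegaven, and the patient is later sent for liver transplant. By the Primary Objective the measure is met. By the Background the disease has progressed. Both statements apply to the same patient, and no sentence settles which prevails. Death after an enzyme fall gives the same result.

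**Step 3. Direction.** The conflict arises only for patients whose enzymes fell first. For them, the enzyme-only count gives success where the Background gives progression. The reverse error cannot arise by this route, so within this mechanism the effect can only favour Omegaven.

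**Step 4. Size per patient.** The protocol says: "We will be enrolling up to 10 patients 0- less than 18 years of age". If a response proportion were reported as responders / n, reclassifying one patient changes it by 1/n. With n at most 10, 1/n is at least 1/10, or 10 percentage points.

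**Step 5. Illustration.** Assumptions not in the protocol: n = 10; 8 patients show an enzyme decrease; k of those 8 die or are sent for liver transplant and are recounted as progressed. The rate is (8 − k)/10, with exact (Clopper-Pearson) 95% intervals.

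| k | Rate | 95% interval |
|---|---|---|
| 0 | 80% | 44.4% to 97.5% |
| 1 | 70% | 34.8% to 93.3% |
| 2 | 60% | 26.2% to 87.8% |
| 3 | 50% | 18.7% to 81.3% |
| 4 | 40% | 12.2% to 73.8% |

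The table shows sensitivity only. Nothing in the protocol indicates which k to expect.

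**The case against.** The strongest reply is that this is a compassionate-use access protocol with no planned analysis and no plan to publish. It contains no responder definition, per-patient classification or success proportion, so no stated quantity is biased. How death or transplant enters the analysis of a laboratory measure is often left to a statistical analysis plan, which may exist and was not available here.

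Part of this stands. The miscount is permitted, not prescribed. A reader might infer that the protocol will overstate success by some definite amount, such as 10 to 30 points. The documents do not support that, because both the proportion and the number of affected patients are assumed.

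It does not dispose of the point. The criterion was not left open: the Primary Objective fixes it, and it conflicts with the Background's own account of progression. The protocol also keeps a record of each subject's response (Records to be kept), and Publication of Research Findings leaves reporting possible.

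Three further inferences should be resisted:

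- **That observation stops at transplant or weaning.** Target Population Specifics sets treatment duration. It does not say that data collection ends, and the patient record could hold later events.
- **That the case must be common because enzymes can fall as a liver fails.** No part of the protocol says so. The Background links hepatic injury only with raised enzymes. What the protocol does support is that the case is foreseeable: patients must have failed standard therapies (Inclusion Criteria), and liver transplant is a written exit.
- **That every transplant is a failure.** The exit sentence also covers short bowel transplant, which the Background does not list as progression of PNALD.

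It can also be argued that a passing dip before referral would not qualify as a decrease when read with the aim. That is a reasonable reading, but with no threshold or time point nothing in the text enforces it.

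**Conclusion.** The concern holds in a limited form. The primary measure is badly fixed: it lets a patient whose enzymes fell, and who was then sent for liver transplant or died, be counted as reversed or halted, against the protocol's own description of progression. Such a patient might be labelled halted rather than reversed, which conflicts with the Background just as much.

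The effect runs in one direction, towards Omegaven. Each affected patient is worth at least 10 percentage points of any proportion based on 10 or fewer patients. This assumes that a proportion is reported and that the patient's enzymes fell before the event. The number of such patients cannot be derived from the protocol, so no total bias can be claimed. The point covers liver transplant and death, not intestine-only transplant. The change should be made, since it is cheap and removes a contradiction in the primary objective.

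**What to change.** Add to the Primary Objective wording such as: a patient who dies, or is sent for a transplant that includes the liver, while on Omegaven is counted as progressed regardless of enzyme values; intestine-only transplant is reported separately.

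Report for every patient, beside the enzyme result, why treatment ended: TPN no longer needed, transplant with its type, or death with its cause.

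The cost is one sentence and one extra item in the existing spreadsheet, drawn from the medical record already in use. The result may look less favourable. Counting all deaths avoids a subjective judgement on attribution but may include deaths not due to liver disease, which is why the cause should be listed. Referral for transplant remains a clinical decision; the rule says only how it is counted and changes no treatment, eligibility or stopping rule.

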#### Inclusion Criteria

1. The patient will be PN dependent and unable to meet nutritional needs solely by enteral nutrition.
2. Patient will be <18 years of age.
3. Direct bilirubin > 2.0mg/dl
4. The patient must have failed standard therapies to prevent progression his/her liver disease.

#### Exclusion Criteria

1. Other causes of chronic liver disease (Hepatitis C, Cystic fibrosis, biliary atresia, and alpha 1 anti-trypsin deficiency).
2. Patients who are allergic to eggs/shellfish
3. Patients who have severe hemorrhagic disorders.

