#### 5. DATA COLLECTION

##### Data Collection Procedures

Patients will be identified by [name] and the Intestinal Rehabilitation/Transplant Team.

All potential patients will be either inpatient admitted under the GI or Surgery Service, or GI or Surgery Services will be consulted. [name] or one of the sub-investigators will be notified by the services (if he is not the attending) that a subject has clinically progressed towards needing the investigational drug. [name] will ultimately decide if a subject meets criteria for enrollment.

When [name] feels a patient will benefit from Omegaven, he or one of the sub-investigators will discuss the protocol with the family and answer all questions. Permission/assent will be obtained by the PI, sub-investigators or coordinator.

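### The only allergy exclusion names eggs and shellfish but not fish, although the intravenous product is made from fish oil, so a child with fish allergy alone is eligible as written

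*Protocol*

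**What the plan says.** The protocol identifies the source of the product twice. The primary objective in section 1 speaks of "using a parenteral fat emulsion prepared from fish oil", and section 2 (Background) states that "Fish oil based emulsions (ie, Omegaven) are available in Europe".

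The Exclusion Criteria have three items: other causes of chronic liver disease, an allergy item, and severe hemorrhagic disorders. The allergy item reads in full "Patients who are allergic to eggs/shellfish". The four Inclusion Criteria cover dependence on parenteral nutrition, age under 18, direct bilirubin above 2.0 mg/dl, and failure of standard therapies. None of them concerns allergy.

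On who is enrolled, Data Collection Procedures says that the investigator "will ultimately decide if a subject meets criteria for enrollment". On length of exposure, Target Population Specifics says that patients "will remain on TPN using Omegaven until they no longer need TPN" or are sent for transplant.

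**The concern.** The authors decided that certain food allergies should bar a child from this intravenous product and made that a firm exclusion. The list they wrote does not match their own description of the product. It names shellfish, which the protocol nowhere gives as a source of the emulsion, and omits fish, which it does. In ordinary usage shellfish means crustaceans and molluscs, so the word does not take in fish.

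What is at stake is patient safety, not inference. The product is given intravenously to patients from birth to under 18 years, and exposure continues for as long as parenteral nutrition is needed or until transplant. Safety of the emulsion is the stated secondary objective. The protocol is to stay open indefinitely, so a gap in the screen would remain for later patients.

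**Working it through.** No statistical figure is involved. The check sets the eligibility criteria beside the product description.

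**Inputs**
- Product source: fish oil (section 1, Primary Objective; section 2, Background).
- Inclusion Criteria: 4 items.
- Exclusion Criteria: 3 items.
- Enrollment ceiling: 10 patients (Target Population Specifics).

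**Count of criteria**
- Total: 4 + 3 = 7.
- Concerning allergy: 1 of 7 (exclusion 2).
- Naming fish, or hypersensitivity to the emulsion or its components: 0 of 7.

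**Test case: a child with known fish allergy, no egg or shellfish allergy, and otherwise typical of the target population**

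| Criterion | Result for this child |
|---|---|
| Inclusion 1: dependent on parenteral nutrition | can be met |
| Inclusion 2: under 18 years | can be met |
| Inclusion 3: direct bilirubin above 2.0 mg/dl | can be met |
| Inclusion 4: standard therapies have failed | can be met |
| Exclusion 1: other chronic liver disease | not triggered |
| Exclusion 2: egg or shellfish allergy | not triggered |
| Exclusion 3: severe hemorrhagic disorder | not triggered |

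The child can satisfy 4 of 4 inclusions and triggers 0 of 3 exclusions, and so is eligible as written.

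**Is the gap closed elsewhere?** The rest of the protocol text available for review contains no general hypersensitivity rule, no contraindication, and no instruction to take a fish-allergy history. Data Collection Procedures has the investigator judge whether the criteria are met, which adds nothing where the criteria are silent. The same section and the section on IRB review and informed consent also refer to the investigator's view that the patient would benefit. That judgement could keep the child out, but neither section ties it to allergy.

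**Size.** At most 10 patients are enrolled. The protocol gives neither a prevalence of fish allergy in this population nor a reaction risk, so no expected number is calculated.

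**The case against.** The strongest reply is that the protocol never establishes fish allergy as a hazard with this emulsion. It does not list the components, mention fish protein or state a contraindication. On that view the step from an oil made from fish to a need to exclude fish-allergic children rests on outside knowledge. This stands as a limit on the size of the risk. It does not remove the mismatch: the protocol chose to screen on food allergy and left out the one animal source it names. If the authors considered fish allergy acceptable, screeners need to be told so.

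Second, this is compassionate use in patients known individually to a specialist team. The investigator decides on enrollment, the product is discussed with the family in person, and exclusion 2 already calls for some food-allergy check. A fish allergy might well come to light. That is fair, and it lowers the chance of harm, but it relies on vigilance and not on a written rule. The consent material was not available for review, so a warning to families there cannot be ruled out. It would in any case not alter the eligibility criteria.

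Third, the sentence "All subjects who could benefit from Omegaven will be included" should not be pressed. It stands under Statistical Considerations, where it mainly explains why no statistical case is made, and it is weak evidence that clinical judgement is overridden. The finding does not depend on it.

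Fourth, an absolute exclusion may be worse for the child than case-by-case judgement, since "Without this treatment, the next step for these patients is short bowel or liver transplant". This is the real cost of the change. The protocol has already accepted the same trade-off for egg and shellfish allergy, so extending it to fish is consistent with the authors' own choice.

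Finally, shellfish may have been meant loosely for seafood. The text does not say so, and if that was the intent, the same rewording expresses it.

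**Conclusion.** The concern holds. As written, the eligibility criteria admit a child whose only known allergy is to fish, although the product is described as made from fish oil.

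The conclusion rests on the plain meaning of shellfish and on the criteria list, which is shown in full. It does not depend on any assumed reaction rate or prevalence. In scale it is a small but real gap in a written safety rule: at most 10 patients are enrolled, few or none may be affected, and nothing changes for the objectives or any analysis. It merits correction because it concerns a safety screen and is cheap to repair, not because harm has been shown to be likely.

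**What to change.** Reword exclusion 2 along these lines: *known allergy to fish, egg or shellfish, or known hypersensitivity to any component of the emulsion*. The visible protocol does not list the components, so those applying the criterion will need the product information to hand.

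The cost is one line of text and the IRB review that the protocol requires for any modification. The clinical cost is that a rare fish-allergic child would lose access under this protocol and face transplant as the next step. If the investigators regard that as too severe, they should state in the protocol that fish allergy is not a bar and how it is to be weighed, so that the decision is explicit.
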